### **7.3.3 Sponsor SAE reporting requirements**

Sponsor/Sponsor representative is responsible for reporting relevant SAEs to the competent authority, other applicable regulatory authorities, and participating investigators, in accordance with ICH guidelines, FDA regulations, and/or local regulatory requirements.

Sponsor/sponsor representative is responsible for reporting unexpected fatal or life-threatening events associated with the use of the trial drugs to the regulatory agencies and competent authorities via telephone or fax within 7 calendar days after being notified of the event.

The Sponsor will report all related, unexpected SAEs, including non-death/non-life-threatening related unexpected SAEs associated with the use of the trial medications to the FDA by a written safety report within 15 calendar days of notification. Reporting to the IRB/IEC will be done according to institutional policy.

### **7.4 Recording of Adverse Events and Serious Adverse Events**

Investigators should use correct medical terminology/concepts when recording AEs or SAEs on the SAE Report Forms and AE CRF. Avoid colloquialisms and abbreviations. All AEs, including those that meet SAE reporting criteria, should be recorded on the AE CRF; AEs that meet the definition of an SAE should additionally be reported following the procedures noted in above sections.

#### **7.4.1 Diagnosis vs. signs and symptoms**

All AEs should be recorded individually in the patient's own words (verbatim) unless, in the opinion of the Coordinating Investigator or designated physician, the AEs constitute components of a recognized condition, disease, or syndrome. In the latter case, the condition, disease, or syndrome should be named rather than each individual sign or symptom. If a constellation of signs and/or symptoms cannot be medically characterized as a single diagnosis or syndrome at the time of reporting, each individual event should be recorded as an AE or SAE as appropriate on the relevant form(s) (SAE Report Form and/or AE CRF). If a diagnosis is subsequently established, it should be reported as follow-up information is available. If a diagnosis is determined subsequent to the reporting of the constellation of symptoms, the signs/symptoms should be updated to reflect the diagnosis.

#### **7.4.2 Persistent or recurrent adverse events**

A persistent AE is one that extends continuously, without resolution, between patient evaluation time points. Such events should only be recorded once on the SAE Report Form and/or the AE CRF, irrespective of severity. (E.g. If a persistent AE becomes more severe or lessens in severity, it should be recorded once with highest grade of severity in CRF/SAE Report Form). A recurrent AE is one that occurs and resolves between patient evaluation time points, and subsequently recurs. All recurrent events should be recorded separately in CRF/SAE Report Form.

#### **7.4.3 Abnormal laboratory values**

Any grade 3 or 4 laboratory abnormalities or any clinically significant grade 1 or 2 hematology or biochemistry laboratory value(s) should be recorded as an AE. Isolated laboratory abnormality without clinical significance should not be captured as AE if confirmed by the investigator. If an

abnormal laboratory value or vital sign is associated with clinical signs and/or symptoms, the sign or symptom should be reported as an AE, and the associated laboratory value or vital sign should be considered additional information that must be collected on the relevant CRF. If the laboratory abnormality is a sign of a disease or syndrome, only the diagnosis needs to be recorded on the SAE Report Form or AE CRF.

#### **7.4.4 Deaths**

Deaths that occur during the protocol-specified AE reporting period that are attributed by the investigator solely to progression of disease will be recorded on the “Trial Discontinuation” CRF and should not be reported as a SAE. All other on- trial deaths, regardless of attribution, will be recorded on an SAE Report and expeditiously reported to the Sponsor.

When recording a serious adverse event with an outcome of death, the event or condition that caused or contributed to the fatal outcome should be recorded as the single medical concept on the SAE report and Adverse Event page of the CRF. If the cause of death is unknown and cannot be ascertained at the time of reporting, record “Death NOS” on the CRF Adverse Event page.

#### **7.4.5 Hospitalization, prolonged hospitalization, or surgery**

Any AE that results in hospitalization of >24 hours or prolonged hospitalization should be documented and reported as an SAE unless specifically instructed otherwise in this protocol. There are some hospitalization scenarios that do not require reporting as an SAE when there is no occurrence of an AE. (See [section 7.3](#))

#### **7.4.6 Pre-Existing medical conditions**

A pre-existing medical condition is one that is present at the start of the trial. Such conditions should be recorded on the General Medical History CRF. A pre-existing medical condition should be recorded as an AE or SAE only if the frequency, severity, or character of the condition worsens during the trial. When recording such events on an SAE Report Form and/or AE CRF, it is important to convey the concept that the pre-existing condition has changed by including applicable description.

#### **7.4.7 Pregnancy, abortion, birth defects/congenital anomalies**

Pregnancy, abortion, birth defects, and congenital anomalies are events of special interest. Please refer to pregnancy [section 7.5.1](#) for specific instructions.

#### **7.4.8 New Cancers**

The development of a new primary cancer should be regarded as an AE and will generally meet at least one of the serious criteria. New primary cancers are those that are not the primary reason for the administration of the study treatment and have developed after the inclusion of the patient into the study. They do not include new lesions of the original cancer. Symptoms of metastasis or the new lesions itself should not be reported as an AE/SAE, as they are considered to be disease progression.

#### **7.4.9 Lack of efficacy**

When there is deterioration in the condition for which the study treatment is being used, there may be uncertainty as to whether this is lack of efficacy or an AE. In such cases, unless the sponsor or reporting physician considers the study treatment contributed to the deterioration of the condition, the deterioration should be considered lack of efficacy and not an AE.

#### **7.5 Protocol-Defined Events of Special Interest**

The following are events of special interest, and will need to be reported expeditiously.

##### **7.5.1 Pregnancy, abortion, birth defects/congenital anomalies**

Female patients who are not of child-bearing potential (see [Appendix B](#)) and female patients of child-bearing potential who have a negative serum pregnancy test within 72 hours prior to C1D1 are eligible for the study. Female patients of child-bearing potential (see [Appendix B](#)), and all male partners must consent to use a medically acceptable method of contraception throughout the study period and for 4 weeks after the last dose of Tenalisib. An approved barrier method of contraception must be discussed with the investigator and documented in source note.

During the course of the trial, all female patients of childbearing potential and pregnant partner of male subjects must contact the treating investigator immediately if they suspect that they may be pregnant (a missed or late menstrual period should be reported to the treating investigator).

If an investigator suspects that a patient may be pregnant prior to administration of trial drug(s), the trial drug(s) must be withheld until the result of the pregnancy test is confirmed. If a pregnancy is confirmed, the patient must not receive any trial drug(s), and must be discontinued from the trial. The outcome of the pregnancy will be monitored as outlined in [Appendix B](#).

If an investigator suspects that a patient may be pregnant after the patient has been receiving trial drug(s), the trial drug(s) must immediately be withheld until the result of the pregnancy test is confirmed. If a pregnancy is confirmed, the trial drug(s) must be immediately and permanently stopped, the patient must be discontinued from the trial, and the investigator must notify the medical monitor and Sponsor Representative as soon as possible. If a patient becomes pregnant while enrolled in the trial, a Pregnancy Form should be completed and faxed to the Sponsor. The outcome of the pregnancy will be monitored as outlined in [Appendix B](#).

Congenital anomalies/birth defects always meet SAE criteria, and should therefore be expeditiously reported as an SAE, using the previously described process for SAE reporting. A Pregnancy Form should also have been previously completed, and will need to be updated to reflect the outcome of the pregnancy.

##### **7.5.2 Overdose**

An overdose is defined as accidental or intentional administration of any dose of product that is considered both excessive and medically important. For purposes of this trial, an overdose will be defined as any dose exceeding the proposed dose of Tenalisib (e.g. > 800 mg).

Symptomatic and non-symptomatic overdose must be reported in the CRF. Any accidental or

intentional overdose with the trial treatment that is symptomatic, even if not fulfilling a seriousness criterion, is to be reported to the Sponsor immediately as an AE. All symptomatic overdose, fulfilling a seriousness criterion is to be reported as an SAE as per the SAE reporting procedure. For patients who experience overdose, treatment should consist of supportive therapy. A decision to interrupt treatment or dose reduction to be taken depending on the symptoms.

### 7.6 Dose Modifications

All dose modifications are graded by the CTCAE v5.0.

**Note:** *If cytopenia events are deemed related to the underlying disease rather than Tenalisib, dose reduction will be done as per the investigator’s discretion.*

Patients may resume Tenalisib, provided that the toxicity has resolved to Grade  $\leq 2$  or baseline. If study drug is delayed  $> 2$  weeks because of an adverse event, re-initiation of treatment need to be discussed with the medical monitor.

At the discretion of the Investigator, a dose re-escalation may be permitted for patients who previously had a dose reduction. Holidays from study drug are discouraged. Any patient in whom similar toxicity recurs at the reduced dose should be discontinued from further Tenalisib treatment. Note: In exceptional case, a patient may be allowed following a careful assessment of benefit and risk by the investigator and with approval from the medical monitor.

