### 3.5 Investigational Medicinal Product

#### 3.5.1 Dosage form and strengths

Investigational Product	Dosage form, strength	Manufacturer
Tenalisib	Tablets; 200 mg and 400 mg.	STA Pharma Co. Ltd.

**Note:** Please refer Investigator's brochure for additional information of Tenalisib.

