**Table 3: Dose Modifications for Hematologic Toxicity**

Worst CTCAE Grade Toxicity	Action to be Taken
HEMATOLOGIC	
Neutropenia (ANC)	
Grade 3 $1.0 \times 10^9/\text{L} < \text{ANC} \leq 0.5 \times 10^9/\text{L}$	Maintain dose level. Monitor ANC at least weekly.
Grade 4 $0.5 \times 10^9/\text{L} < \text{ANC}$	First incidence: Hold* dose until resolved to $\leq$ Grade 2 or baseline, Restart Tenalisib at 400 mg BID dose level. Subsequent occurrence: Hold dose until resolved to $\leq$ Grade 2 or baseline, consider growth factor support. Discontinue if further dose modification required.

Grade 3 Febrile neutropenia ANC <1000/mm  with a single temperature of > 38.3 0C (101 0F) or a sustained temperature of ≥ 38 0C (100.4 0F) for more than one hour.	Hold* dose until resolved to ≤ Grade 2 or baseline, consider growth factor support, then reduce by 1 dose level.
Thrombocytopenia	
Grade 3 (50.0 X 10  /L < PLT ≥ 25.0 X 10  /L)	Maintain dose level. Monitor platelet count at least weekly.
Grade 4 25.0 X 10  /L < PLT	1st occurrence: Hold** dose until resolved to ≤ Grade 2 or baseline, Restart Tenalisib at 400 mg BID dose level. Subsequent Occurrences: Hold dose until to ≤ Grade 2 or baseline, consider platelet transfusion as necessary. Discontinue if further dose modification required. Note: If the count is <50 X 10  /L before initiation of therapy (e.g. in case of marrow involvement), the dose reduction should be done as per investigator's judgement.

\*If study drug is delayed >2 weeks because of an adverse event, treatment strategy should be discussed with medical monitor.

\*\* Patient receiving concomitant medication (e.g. anticoagulants, anti-platelets, aspirin, or low molecular weight heparin) must be discussed with the medical monitor for continued management.

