Diarrhea	
Moderate:
 
 
• Maintain Tenalisib dose. Monitor at least weekly until resolved.
 
 
Severe diarrhoea or hospitalization
 
 
• Withhold Tenalisib dose. Monitor at least weekly until resolved.
 
• Restart Tenalisib at 400 mg BID dose level.
 
 
Life threatening diarrhoea
 
 
• Discontinue Tenalisib permanently.
 

Cardiac	
If a QTcF <math>>500</math> msec has been demonstrated, hold dose.
 
The patient will be monitored hourly with ECGs until the QTcF <math><500</math> msec and the QTcF has returned to “<math><30</math> msec from baseline”. Immediate attention to potassium and magnesium and other clinical factors such as oxygenation and ischemia should be addressed.
 
All cardiac events should be treated as per the local standard of care and referral to a specialist if clinically indicated. Any final decisions concerning dose modifications or permanently discontinuing the patient from study drug due to QTcF prolongation will occur after discussion with medical monitor.

OTHER NON-HEMATOLOGIC	Action to be Taken
Grade 3/4 CTCAE	
First occurrence:
 
Hold* dose until toxicity Grade <math>\leq 2</math>; restart Tenalisib at 400 mg BID dose level.
 
Subsequent Occurrences: Hold dose until to <math>\leq</math> Grade 2 or baseline.
 
Discontinue if further dose modification required.

\* If study d\*If the drug is delayed  $>2$  weeks because of an adverse event, treatment strategy should be discussed with medical monitor.

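### Section 7.6 and three rows of Tables 3 and 4 set different defaults when similar toxicity recurs at 400 mg BID, and the dose step in the febrile neutropenia row is undefined

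*Protocol*

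**What the plan says.** Section 7.6 gives a general rule for recurrence: "Any patient in whom similar toxicity recurs at the reduced dose should be discontinued from further Tenalisib treatment". A note adds that, in an exceptional case, "a patient may be allowed following a careful assessment of benefit and risk by the investigator and with approval from the medical monitor". The same section says that, at the investigator's discretion, "a dose re-escalation may be permitted for patients who previously had a dose reduction".

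In Table 3, the Grade 4 neutropenia row holds the drug at the first event and then says "Restart Tenalisib at 400 mg BID dose level". For a subsequent occurrence it holds again until recovery, then adds "consider growth factor support. Discontinue if further dose modification required". The Grade 4 thrombocytopenia row follows the same pattern, with platelet transfusion in place of growth factor. In Table 4, the row for other Grade 3/4 non-hematologic toxicity also restarts at 400 mg BID after the first event. It holds again on later events and ends "Discontinue if further dose modification required".

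The Grade 3 febrile neutropenia row in Table 3 names no dose. It says to hold, "consider growth factor support, then reduce by 1 dose level". Section 3.5.1 lists the product as "Tablets; 200 mg and 400 mg".

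**The concern.** Take a patient restarted at 400 mg BID after Grade 4 neutropenia who has Grade 4 neutropenia again at that dose. Under Section 7.6 the default is to stop, and continuing needs a benefit-risk assessment and the medical monitor's approval. Under Table 3 the default is to hold and wait for recovery, with no approval sought. Two sites could each follow the protocol and manage the same patient in opposite ways. One would re-expose a patient to the drug after repeat severe toxicity; the other would withdraw that patient.

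The reported results would differ too. SAP Section 10.6.2 counts TEAEs leading to discontinuation and TEAEs leading to dose interruptions as separate lines. Section 10.1 reports reasons for discontinuation and the number of patients with reductions or interruptions. Section 10.6.1 calculates exposure as last dosing day minus first dosing day plus one, so a patient who is held and then resumes accrues the held days and all later days, while a patient who is stopped does not. Safety and tolerability is the secondary objective, so these tables carry its conclusion.

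**Working it through.** The plan gives no figure to reproduce, so the check is a row-by-row comparison with Section 7.6.

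| Row | After the first event | On recurrence | Against Section 7.6 |
|---|---|---|---|
| Grade 4 neutropenia (Table 3) | Hold, restart at 400 mg BID | Hold again; stop only if further modification is needed | Conflicts |
| Grade 4 thrombocytopenia (Table 3) | Hold, restart at 400 mg BID | Hold again; stop only if further modification is needed | Conflicts |
| Other Grade 3/4 non-hematologic (Table 4) | Hold, restart at 400 mg BID | Hold again; stop only if further modification is needed | Conflicts if the toxicity is similar |
| Transaminitis (Table 4) | Withhold, restart at 400 mg BID (Grade 3) | Stop permanently after weighing risk and benefit | Agrees |
| Febrile neutropenia (Table 3) | Hold, step down one unlisted level | No instruction | Step undefined |
| Renal, bilirubin, infection, diarrhea (Table 4) | Varies | No instruction | Section 7.6 stands alone |
| Cardiac (Table 4) | Hold | Final decision after discussion with the medical monitor | No direct conflict |

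The Grade 3 neutropenia and Grade 3 thrombocytopenia rows maintain the dose, so no reduced dose arises from them. Three rows conflict and one agrees. No text says whether the tables or Section 7.6 takes precedence.

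**When the conflict arises.** All of these must hold:
1. The investigator judges the event related to the drug (Section 7.6.2 limits the tables to such events).
2. The event falls in one of the three rows.
3. The toxicity is similar to the earlier one.
4. The patient is still at 400 mg BID and has not been re-escalated.

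Medical monitor discussion is otherwise triggered only by a delay of more than 2 weeks or, for thrombocytopenia, by certain concomitant drugs. A shorter second hold needs no contact.

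**Dose level.** From 800 mg BID, the other rows imply that one step down is 400 mg BID, because that is the only reduced dose the tables name. For a patient already at 400 mg BID there are two cases. If the earlier event was similar, Section 7.6 points to stopping while the row still reads as a further step down. If the earlier event was a different toxicity, Section 7.6 does not apply, and the row sends the patient to a level that is not listed.

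**Size.** With n patients in the safety set, one patient moves a rate by 100/n percentage points: 100/20 = 5.

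Protocol Section 1.1.2 gives a rough sense of how often a first event might occur. In the T-cell lymphoma study, 49 patients were treated. The listed related Grade 3 or higher events that could fall in the three rows are neutropenia 3, rash 3, hypophosphatemia 1, raised INR 1 and diplopia 1: 3 + 3 + 1 + 1 + 1 = 9. Scaled to 20 patients, 9/49 × 20 ≈ 3.7 first events. This uses another disease and mixed doses, and assumes each event is a separate patient. It also overcounts neutropenia, since only Grade 4 reaches the disputed row. The commonest such event, AST/ALT elevation (11), belongs to the row that agrees with Section 7.6. The documents give no recurrence rate at 400 mg BID, so the number of patients affected cannot be estimated.

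**The case against.** The best defence is that little room is left for conflict. Section 7.6.2 calls the tables guidelines. Section 4.3 already leaves withdrawal for Grade 3/4 non-hematologic toxicity to the investigator's opinion. A subsequent occurrence could mean one after re-escalation, and the second hold could itself count as a further modification, which would lead to stopping. These points narrow the conflict but do not remove it. The tables do not mention re-escalation. They do not define further modification, and if the second hold counted as one, the instruction to hold until recovery would have little purpose. Discretion under Section 4.3 does not tell a site which default applies.

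Three stronger readings are tempting, and the documents do not support them:

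- A reader might infer that every second event in the three rows is affected. Section 7.6 covers only similar toxicity at the reduced dose. A different Grade 3/4 toxicity, or a recurrence after re-escalation, falls under the table alone.
- A reader might infer bias in PFS and duration of response, because Table 1 shows no scans after the end-of-treatment visit. Section 8.2 continues imaging until progression, new anti-cancer treatment, consent withdrawal, death or end of study. Stopping the drug is not on that list.
- A reader might infer that one level below 800 mg BID could be 600 mg BID. That rests on the 200 mg tablet alone; no passage offers it as a reduction.

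It also stands that safety is descriptive, there are no formal hypotheses, and the SAP records closure after Part 1 for lack of response. Nothing in the efficacy conclusion is shown to depend on this point.

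**Conclusion.** This is an internal inconsistency in the protocol, of moderate weight. Section 7.6 and three table rows give different default actions for related, similar toxicity that recurs at 400 mg BID without re-escalation. The febrile neutropenia row adds an undefined term, which matters only for a patient already at 400 mg BID.

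The main consequence is for patients: the same repeat severe toxicity can lead to re-exposure or to withdrawal, depending on which text a site follows. In the analysis, it blurs the split between interruptions and discontinuations, and with it disposition and exposure. The 5 points per patient assume that all 20 planned patients are in the safety set; a smaller set makes each patient count for more. Whether any patient met all the conditions cannot be told from the documents.

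**What to change.** Reconcile the recurrence rule in Section 7.6 with the subsequent-occurrence lines of the three rows, so that one action applies to similar toxicity recurring at the reduced dose. State whether a repeat hold counts as a further modification, and how the rule applies after re-escalation. Define the permitted dose levels once, or replace the term in the febrile neutropenia row, and cover the patient who is already at the reduced dose. The choice of rule and level belongs to the sponsor's clinicians.

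The cost is a clarification of one paragraph and four table cells, with no added procedures. Since the study closed after Part 1, the remaining benefit is consistent classification in the study report and sound text if this section is reused. The report should state how any recurrence at 400 mg BID was handled and counted.

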#### 7.6.1 Criteria for starting Tenalisib new cycle

If treatment is delayed  $> 2$  weeks due to AE or any other reason, treatment to be resumed with new cycle after discussion with medical monitor as long as:

- Absolute neutrophil count has returned to baseline, or  $> 750/\mu\text{L}$ . Platelet count is  $> 50,000/\mu\text{L}$ .
- Recovered from grade 3-4 non-hematologic toxicity to grade 2 or baseline (excluding alopecia). Treatment may be delayed for up to 2 weeks to recover from toxicity.
- No clinical or radiographic evidence of disease progression.

